The escalation of care for patients in a hospitalized setting between nurse practitioner managed services, teaching services, step-down units, and intensive care units is critical for appropriate care for any patient. Often such "triggers" for escalation are initiated based on the nursing evaluation of the patient, followed by physician history and physical exam, then augmented based on laboratory values. These "triggers" can enhance the care of patients without increasing the workload of responder teams. One of the goals in hospital medicine is the earlier identification of patients that require an escalation of care. We have developed a model through a retrospective analysis of the historical data from the Mount Sinai Data Warehouse (MSDW), which can provide machine learning based triggers for escalation of care (Approved by: IRB-18-00581). This model is called "Medical Early Warning Score ++" (MEWS ++). This IRB seeks to prospectively validate the developed model through a pragmatic clinical trial of using these alerts to trigger an evaluation for appropriateness of escalation of care on two general inpatients wards, one medical and one surgical. These alerts will not change the standard of care. They will simply suggest to the care team that the patient should be further evaluated without specifying a subsequent specific course of action. In other words, these alerts in themselves does not designate any change to the care provider's clinical standard of care. We estimate (see "Narrative" section for details) that this study would require the evaluation of ~ 18380 bed movements and approximately 30 months to complete, based on the rate of escalation of care and rate of bed movements in the selected units (9W, 9E, 10W, 10E).

IF Number

IF2411760

2. Summary - Setup

Funding Has Been Requested / Obtained	No
Application Type	Request to Rely on Mount Sinai IRB
Research Involves	Prospective Study ONLY
Consenting Participants	No
Humanitarian Use Device (HUD) Used Exclusively in the Course of Medical Practice	No
Use of an Investigational Device to Evaluate Its Safety or Effectiveness	No
Banking Specimens for Future Research	No
Cancer Related Research that Requires Approval from the Protocol Review and Monitoring Committee (PRMC).	No

Is this Cancer Related Research? Cancer Related Research is defined as research that has cancer endpoints or has a cancer population as part of or all of its targeted population. This includes protocols studying patients with cancer or those at risk for cancer.

Clinical Trial	Yes
----------------	-----

**** A prospective biomedical or behavioral research study of human subjects that is designed to answer specific questions about biomedical or behavioral interventions (drugs, treatments, devices, or new ways of using known drugs, treatments, or devices).
* Used to determine whether new biomedical or behavioral interventions are safe, efficacious, and effective.***

Drugs / Biologics	No
-------------------	----

**** Drugs / Biologics That Are Not a Part of Standard Practice
* Controlled Substances
* Drugs / Biologics Supplied by the Research Sponsor or Purchased with Study Funds***

Ionizing Radiation for imaging or therapy, including X-Ray, Fluoroscopy, CT, Nuclear Medicine, PET andor Radiation Therapy:

* Purely for standard of care:	No
* In frequency or intensity that exceeds what is necessary for standard of care:	No

Hazardous Materials	No
---------------------	----

**** Recombinant DNA
* Viral Vectors
* Plasmids
* Bacterial Artificial Chromosomes***

*** Toxic Chemicals, Potentially Toxic Medications, Carcinogens
* Autologous Cell Lines**

**Request Use of Clinical Research No
Unit Resources**

3. Summary - Background

Objectives

Mount Sinai Hospital has developed a Rapid Response Team (RRT) system designed to give general floor care providers additional support for patients who may be requiring a higher level of care. This system enables both nurses and physicians to notify the RRT and have a critical care team evaluate the patients. During the period of 03/01/2018 to 09/17/2018, Mount Sinai Hospital floor units on 10W and 10E units made 357 rapid response team (RRT) calls with only 58 leading to an actual increase in the level of care (true positive rate ~ 16%). Similarly, the Electronic Health Record (EHR) generated 839 sepsis Best Practice Alerts (BPAs) yet only five led to escalations in care (true positive rate ~ 0.5%). The results above would imply that over 168 evaluations need to be made to identify a single case where the patient required an escalation in care. The goal of ReSCUE-ME is to evaluate prospective model performance and identify the best spot which we can incorporate MEWS++ into RRT and Primary providers workflow. The primary endpoint is rate of escalation of care on 10W and 10E during the study period.

Background

In a prior study, our group has demonstrated that a machine learning model (MEWS++) significantly outperformed a standard, manually calculated MEWS score on a large retrospective cohort of hospitalized patients. To develop this model, we used a data set (Approved by: IRB-18-00581) of 96,645 patients with 157,984 hospital encounters and 244,343 bed movements. We found that MEWS++ was superior to the standard MEWS model with a sensitivity of 81.6% vs. 44.6%, specificity of 75.5% vs. 64.5%, and area under the receiver operating curve of 0.85 vs. 0.71. Encouraged by this prior result, we are seeking to evaluate our model in a prospective study.

A silent pilot of the ReSCUE-ME alerts has been running on 10E and 10W since Feb 2019. We have been continuously monitoring the alert performance via a real-time web-based dashboard. The results are summarized below:

- Median # of alerts to primary team, per floor, per day: 8
- Median # of alerts to RRT, per floor, per day: 4
- Sensitivity 0.76, Specificity 0.68, AUC 0.77
- Accuracy 0.69, Precision 0.3, F1 Score 0.43

This performance compares very favorably to the performance seen in the retrospective historical cohort used to develop the MEWS++ model:

- Sensitivity 0.82, Specificity 0.76, AUC 0.85
- Accuracy 0.76, Precision 0.12, F1 Score 0.19"

Primary and Secondary Study Endpoints

Primary Endpoints:

- Composite of the Rate of escalation of care (from floor to Stepdown, Telemetry, ICU) and rate of RRT initiated therapy (including but not limited to blood pressure support, respiratory care support, anti-biotic augmentation, invasive monitoring) in the selected units (10E and 10W)

Secondary Endpoints:

- Blood pressure support utilization (e.g., initiation of vasopressor medication, administration of fluid bolus)
- Respiratory care support utilization (e.g., nasal cannula to high flow)
- Accuracy of predicting care escalation from the floor to ICU, step-down, and Telemetry
- Cardiac arrest/mortality rate in 10E and 10W compared with two control units (9W and 9E)
- Evaluate the average calls per day and average calls per patient when compared to historical and matched general medical-surgical floor units (9W and 9E)
- Evaluate through a survey format of nursing and physician care providers the utility of MEWS++ scoring in determining whether or not an RRT call should be placed. This survey will be administered at the beginning and end of the enrollment period through an online REDCap form hosted within our institution (or comparable system). The survey will be administered by one of the co-investigators within the study.

**Protocol Was Already Approved
by the Icahn School of Medicine at
Mount Sinai (ISMMS) Institutional
Review Board (IRB) Under a
Different Principal Investigator**

No

**Protocol Was Previously Submitted No
to an External(non-ISMMS) IRB**

4. Research Personnel

Name/Department	Role/Status	Contact	Access	Signature Authority	Phone	Email
[name] / Anesthesiology	PI / Faculty	Yes	SIGNAUTH			
[name] / Pharmacology and Systems Therapeutics	Co-Investigator /	Yes	EDIT		[contact]	
[name] / Surgery	Co-Investigator /		EDIT			
[name] / Surgery	Co-Investigator /		READONLY			
[name] / Office of Clinical Research	Co-Investigator /		READONLY			
[name] / Surgery	Co-Investigator /		EDIT		[contact]	
[name] / Surgery	Co-Investigator /		READONLY		[contact]	
[name] / IT Department	Co-Investigator /	Yes	EDIT			
[name] / IT Department	Project Director /		READONLY			
[name] / Anesthesiology	Co-Investigator /		READONLY			
[name] / Neurology	Co-Investigator /		READONLY			
[name] / Anesthesiology	Co-Investigator /		READONLY			

5. Sites

Site Name The Mount Sinai Hospital

Other External Site Name

Contact Details

Approved

Approval Document

Funded By Mount Sinai

Other IRB

6. Subjects - Enrollment

Site Name The Mount Sinai Hospital
Subjects To Be Enrolled
18680
Total Number of Subjects to be Enrolled Across All Listed Sites Above (Auto Populated) 18680

7. Subjects - Setting and Resources

Setting of Human Research Other

Specify Other Setting of Human Research

Hospital Units on 10W, 10E, 9W, 9E.

Total Number of Subjects Needed 18680

To Complete Study

Feasibility of Meeting Recruitment Goals

Our initial observation shows the rate of escalation ~ 10% for the selected units (10W and 10E). The estimated sample size is ~ 934 escalations of care which we expect to observe by including ~9340 bed movements. The estimated bed movements per day in the selected units is ~ 10 which makes the expected pilot days ~ 934 days (~ 2.5 yrs.). We anticipate an equal number of escalations for 9W and 9E, which will not receive any MEWS++ alerts.#

Facilities To Be Used for Conducting Research

Hospital Units on 9W, 9E, 10W, 10E

Multi-Center Study No

Community-Based Participant Research Study No

PI must attest to the following.

**** Process is adequately described to ensure that all persons assisting with the trial are adequately informed about the protocol, the investigational product(s), and their trial-related duties and functions.***

8. Subjects - Populations

Inclusion Criteria

All patients age 18 or greater who were admitted to a general care unit on 9W, 9E, 10W, 10E.

Exclusion Criteria

Any admitted patient who has a "Do Not Resuscitate (DNR)" and/or a "Do Not Intubate (DNI)" order in the EHR, any patient made "level of care" by RRT as documented in REDCap.

Enrollment Restrictions Based No

**Upon Gender, Pregnancy,
Childbearing Potential, or Race**

Age Range(s) 18 to 64 Years, 65 Years and Over

Targeted Population(s) Adults - Patients

Other Aspects that Could Increase Subjects Vulnerability

Prisoners and non-laboring pregnant women will be included if they are admitted to 10E/W or 9E/W. This will be rare but possible. Incapacitated patients will be provided the study information sheet within their paper chart and included unless their health care proxy/legally authorized representative chooses to opt them out of the study. If they were to regain consciousness and capacity, then they would have the ability to withdraw from the study."

Safeguards to protect Subjects rights and welfare

All key personnel have been HIPAA trained. All data will be encrypted and stored on secure servers within the hospital data center, with access restricted based on involvement in the project. Patients will also be offered multiple methods of withdrawing participation consent from the study, which includes by phone, email, website, and nursing care.

9. Subjects - Participation

Duration of an Individual Subjects Participation in the Study

During the entirety of their care on 9W, 9E, 10W, 10E

Duration Anticipated to Enroll All Study Subjects

We anticipate, given the current volume of bed movements, that it will take 30 months to complete enrollment.

Estimated Date for the Investigators Within 3-5 years
to Complete This Study

Procedures for Subjects to Request Withdrawal

Subjects may also withdraw from permission for the use and disclosure of any of your protected information for research and can do so by contacting the unit business associate "BA", by email to [contact] or by calling to [contact] with the information specified in "Waiver Information Sheet" (Appendix 1).

Procedures for Investigator to Withdraw Subjects

The Principal Investigator may stop subject involvement in this research study at any time without subject consent. This may be because the research study is being stopped, the instructions of the study team have not been followed, the investigator believes it is in their best interest, or for any other reason.

"Not participate" or "withdraw" means the alerting will be suppressed/turned off for the patient, their data will not be collected, and no alerts will be sent. Any data or alerts prior to withdrawal will be retained. This information has been added to the consent.

Participants Will Be Recruited Yes

Recruitment Method(s) Clinical Practice

How Participants Will Be Identified

All patients admitted to 10E, 10W, 9E, and 9W

Who Will Initially Approach Potential Participants Clinic Personnel

How Research Will Be Introduced to Participants

Description of the study protocol will be given to participants upon admission to the floor. We will instruct the Business Associate and nursing team members to specifically call to attention to the provided information sheet when a patient is admitted to the unit. We will also post prominent printed notices describing the study throughout the unit (e.g. on the walls near the nursing desk, on any bulletin boards designed for patient communication, etc). Furthermore, if a patient does trigger an alert, the RRT staff will be instructed to notify the patient of the information sheet. Finally, upon discharge, the information sheet would be provided again to the patient as part of their check-out. As such, there exists at least 3 touch points for the patient to discuss the study with a care provider.

How Participants Will Be Screened

Automated screening by the software that generates alerts.

10. Subjects - Risk and Benefits

Risks to Subjects

The MEWS++ alerts will serve to notify the care team of a potential deterioration in a patient's clinical condition. What the provider may choose to do with the MEWS++ alert is left completely to their discretion and we do not propose any determination of care by the MEWS++ alert. As a result, there will be no alteration in the standard of care. All therapeutic interventions will be at the discretion of the care providers and the expected risk of monitoring for select individuals within the interventional cohort should be minimal. The potential risk of breach of confidentiality or loss of protected healthcare information (PHI), will be unlikely as all data will be password protected and any patient identifiers will be encrypted; furthermore, all data gathering will be done on Mount Sinai internal network computers and devices.#

We do not change any workflow for the primary team and RRT. We just increase awareness in the clinicians' mind that a patient may be in danger of deterioration. The primary intervention by the Primary team is simply to increase the frequency of vitalsigns measurement. This will not be associated with any risk or patient safety concerns. We will not remove any of current notifications being received by RRT we will just add one more notification to the current workflow.

One possible risk is alert fatigue. The primary cause of alert fatigue for the RRT team is currently the "Sepsis BPA" generated by Epic, not clinician generated alerts or the alerts that will be generated by this study. The alerting protocol attached to the application was carefully designed to minimize the number of additional alerts. Based on our modeling we anticipate 5 additional alerts to RRT per additional 12-hour shift. This is confirmed by the silent pilot. This was extensively discussed with both nursing and RRT leadership who agreed that the burden of this additional alerting is tolerable. The Sepsis BPA's generate far more alert fatigue. They are being modified to fire less frequently, as part of a non-IRB approved PI/QI changes being made directly by the CMO's office and Epic implementation team, independent of this protocol.

In order to minimize alert fatigue from our alerts, we will be continuously trending the alert burden of the study via the web dashboard and other custom analytic tools. In addition, care provider participants will be polled for their degree of alert fatigue. A review committee will be formed to assess the need to adjust the degree of alerting.

Currently the RRT team and floor nurses are overburdened by Sepsis BPA alerts. Our alerts are more sensitive and more specific and are carefully calibrated to fire less often based on both the retrospective data used to develop the alert and our silent pilot. c. Since the number of alerts is fairly low (5 alerts per 12 hours per floor) and the refractory period can be adjusted automatically based on the clinicians' judgment (see below), we don't believe we will encourage "over testing".

It should be noted that over testing is often a result of inability to ignore results of alerts without perceived medicolegal ramification. By the very fact that our alert is investigational, it would not produce similar concerns.

Inducing a false sense of security is perhaps unavoidable with the introduction of any new monitoring modality. During our education sessions with providers, it will be stressed that MEWS++ is an investigational alert and it should not override clinical judgement. We will have two further mechanisms for soliciting clinician feedback and ensuring a false sense of security is not imbued in the staff. First, we will be in close communication with nursing and RRT leadership throughout the pilot, via check-in meetings initially weekly, and then monthly or as needed throughout the study. Second, the RRT team logs details of every RRT visit to a REDCap database. These data are automatically integrated into our analysis pipeline. We match alerts to RRT calls as part of our performance monitoring. If a deterioration occurs that is missed by our algorithm but seen by RRT, will be able to analyze and understand what factors may have contributed to the miss, and if alert fatigue or a false sense of security contributed to the miss.

Description of Procedures Taken to Lessen the Probability or Magnitude of Risks

No additional data will be gathered beyond that of the standard of care for patients, thus limiting risks of the additional information. The research personnel table lists all personnel who may obtain viewing privileges to the collected data.

Provisions for Research Related Harm / Injury

There is no risk of research related to harm or injury as no therapeutic intervention is made based on the results from this study's evaluation. All participant will receive standard of care interventions.

Expected Direct Benefit to Subjects

As a direct benefit from enrolling in this study, we expect the subjects will be more closely monitored for deterioration in clinical condition and will receive more immediate escalation in care when compared to both historical and matched control subjects.

Benefit to Society

We hope that the proposed technology will prove to have a highly sensitive and specificity for predicting individuals who are at risk of clinical deterioration and may require a higher/more intensive level of care. If this does prove to be true, this would be a significant advance to the field of medicine. It would help to reduce death within an inpatient hospital setting.

Provisions to Protect the Privacy Interests of Subjects

By only allowing only members of the investigational team to access PHI we protect subjects' privacy. All study personnel has completed HIPAA training, which ensures the utmost care is used to handle PHI.

Economic Impact on Subjects

There is no economic burden on the patient.

11. Procedures - Narrative

Description of the Study Design

Patients admitted to 10W and 10E meeting the inclusion and exclusion criteria will undergo a modified RRT evaluation protocol as detailed in Appendix 4: Process Flow. In brief, the patient will be evaluated based on our retrospectively validated machine learning algorithm (MEWS++) designed to improve identification of patients who may need care escalation. Patients on 9W and 9E will be followed but no alerts, interventions or changes from standard of care will be pursued. The study is designed to evaluate the equivalence in the proportion of escalations between the standard of care RRT protocol and our proposed ReSCUE-ME protocol. Patients admitted to 9W and 9E will not undergo any additional monitoring and thus will serve as controls.

Further details of the alerting system are listed below.

- a. Notifications can be suppressed or re-enabled on a per-patient basis. This is a core feature as it is needed to fulfill the opt-out process that we documented in our application's appendices.
- b. Currently there are several automated alerts sent to Vocera. These include ventilator and telemetry alarms, e.g. an alarm if the ECG monitor detects asystole. There is also a simple rules-based Epic BPA for hyperkalemia that sends an alert to the Vocera if a patient's potassium level is high. There is an administrative policy on alarm management that covers these existing alerts - Clinical Alarm Management GPP-242 – link to policy below: <http://policies.mountsinai.org/web/general-policies-and-procedures/policies/-/policy-management/viewPolicy/565852/>.

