Description of the Source Records that Will Be Used to Collect Data About Subjects

For each patient, real-time data from the EHR, the admitting system (Cerner ADT), the ECG (MUSE), and laboratory information systems (SCC) will be ingested by the ReSCUE-ME engine and used to generate a prediction score. Additional information provided by the RRT team on the result of the RRT intervention will be extracted from REDCap. These values as specified in Appendix 3 will be processed through the ReSCUE-ME data streaming engine to generate a MEWS++ score for patients who have not been excluded or withdrawn from the study. If an individual withdraws participation from the study, all data pertaining to this patient's current visit will be removed from

ReSCUE-ME. Clinical documents may also be assessed for the purpose of further clarification of events during the RRT intervention.

Description of Data that Will Be Collected Including Long-Term Follow-Up

The data that will be collected during this study include vitals, electrocardiogram, laboratory data, clinical evaluations, and patient demographics from ADT, Epic, MUSE, and Laboratory Information System. A detailed list is provided in Appendix 3. At this time we do not plan on conducting long-term follow-up upon the discharge of the patient from their current hospital visit.

Research Requires HIV Testing No

12. Procedures - Genetic Testing

Genetic Testing Will Be Performed No

Guidance and Policies > Future Use Data Sharing and Genetic Research

13. Procedures - Details**Surveys or Interviews** Yes**Type of Instruments Being Used** Created By Research Team**Description of Instruments Created By Research Team**

A REDCap survey will be created to understand the impact of the alerts on the RRT team. This clinician survey has not yet been developed. We will not do this piece of the research until the survey has been approved by the IRB and the protocol modified appropriately and also approved.

Audio / Photo / Video Recording No**Deception** No**Results of the Study Will Be Shared** No
with Subjects or Others

14. Procedures - Instruments**Instruments Created By Research Team**

Type	REDCap RRT survey
Name	REDCap RRT survey
Upload	REDCap RRT Survey Placeholder.docx

15. Procedures - Compensation

Compensation for Participation No

16. Consent - Waiver of Informed Consent

Requesting Waiver For

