Receipt or Transmission of Data	No
Holding Code That Can Be Linked to Identity of Participants	No

Duration Data Will Be Stored

Data are stored in accordance with the data retention policy of the manuscript in which the results will be published. This may vary by publication but is generally 7 years.

Steps That Will Be Taken to Secure the Data During Storage, Use, and Transmission

Only the designated investigator and co-investigators as listed on this form will have access to patient data used in this study and will be the sole arbiters for receipt and transmission of this data. The data will be password protected on Mount Sinai computers. Data are encrypted both at rest (i.e., when stored in the database) and while in motion (i.e., during transit between various components of the alerting system) using industry standard encryption protocols. Data will only be accessed from within the Mount Sinai network to ensure confidentiality, which is also password protected and physical access restricted. Any presentation will separate the presented material from the associated identifiers. All individuals have completed institutionally approved HIPAA training.

Power Analysis/Data Analysis Plan (Including Any Statistical Procedures)

Sample size calculation

Based on the pilot feasibility study, the current true rate of escalation of care in the selected units is ~ 10%. We expect that MEWS++ will identify at least 50% of the escalations, on average ~ 6 hrs before the expected time of deterioration/escalation. It is estimated that RRT and front-line providers collaboratively will be able to prevent ~ 20% of the predicted escalations. We are specifying a non-inferiority or superiority margin of 5%. As a result, the estimated sample size needing to achieve a type 1 error of 5% and power of 95% is 934. based on the rate of escalation ~ 10%, a total of approximately 9340-bed movements will need to be recruited for this study in the MEWS++ group and a total of 18680-bed movements across both groups. We assumed that there is not a significant

difference in the escalation rate between the selected units (10E and 10W) and control units (9E and 9W). Interim evaluations every 6 month will be conducted and if at any point the model meets statistical significance or major flaws identified, a subsequent report will be submitted.

Statistical Analysis:

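### Two different primary endpoints are named, and the final SAP analyses no composite, labels no escalation model as primary and does not record that the composite was dropped

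*Combined protocol and SAP*

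**What the plan says.** The protocol states the primary endpoint twice within section 3 (Summary - Background). Under Objectives: "The primary endpoint is rate of escalation of care on 10W and 10E during the study period". Under Primary Endpoints: "Composite of the Rate of escalation of care (from floor to Stepdown, Telemetry, ICU) and rate of RRT initiated therapy", with the therapy component described by an open-ended list. How the two components combine is not stated.

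The rest of the protocol works with escalation alone:

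- Section 11, Description of the Study Design: "The study is designed to evaluate the equivalence in the proportion of escalations".
- Section 7, Feasibility: "The estimated sample size is ~ 934 escalations of care which we expect to observe by including ~9340 bed movements".
- Section 19, Sample size calculation: starts from a 10% escalation rate, expects at least half of escalations to be identified, and adds "It is estimated that RRT and front-line providers collaboratively will be able to prevent ~ 20% of the predicted escalations". It sets a 5% margin for non-inferiority or superiority, whereas section 11 speaks of equivalence.

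The Final Protocol statement says that nothing was changed during the study.

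The original SAP gives a non-exhaustive menu of tests and ties none to the primary endpoint. The final SAP (December 2021), Patient Level Analysis, has an IPTW negative binomial model for the number of escalations over the whole stay and an IPTW logistic model for ever being escalated. Covariate-adjusted versions are labelled confirmatory. Blood pressure support, one named part of RRT therapy, is modelled as a count of its own.

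In the Summary of Changes, the Primary outcome entry covers first hospitalisation, assignment by initial arm, and IPTW. It does not name the outcome. The secondary-outcome table gives a reason for each removal, including respiratory support (20 orders across both groups). ICU escalation within 12 and 24 hours is listed as ad hoc.

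**The concern.** The two endpoints are not minor variants of one measure. The alerts call in the RRT, so an escalation may be averted because the RRT treated the patient on the floor. That patient leaves the escalation endpoint but stays in the composite. The same trial data can therefore look favourable on one endpoint and neutral on the other.

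The final SAP is written in the past tense and cites observed counts. With the endpoint, the model and the hypothesis all left open at that stage, the plan gives no protection against choosing the primary result after the results are known. A reader also cannot learn from the change log that a listed primary endpoint went unanalysed, or why, although the same log explains each removed secondary outcome.

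**Working it through.** **1. The statements side by side**

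| Place | Endpoint | Hypothesis or margin |
|---|---|---|
| Section 3, Objectives | Escalation | None |
| Section 3, Primary Endpoints | Escalation plus RRT-initiated therapy | None |
| Section 11, Study Design | Escalation | Equivalence |
| Section 19, Sample size | Escalation, 10% | Non-inferiority or superiority, 5% |
| Final SAP, Patient Level Analysis | Escalation count; ever escalated | None |
| Summary of Changes, Primary outcome | Not named | None |

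**2. Which endpoint was sized?** Inputs from section 19: rate 10%, margin 5% (taken as absolute points), type 1 error 5%, power 95%, stated n 934. The non-inferiority formula with no true difference is

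n per group = (z₁ + z₂)² × 2p(1 − p) / margin² = (1.960 + 1.645)² × 2 × 0.10 × 0.90 / 0.05² = 935.6, about 936.

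This reproduces 934 within rounding of the z values, so the size rests on the escalation proportion. It does not show which hypothesis was meant. Non-inferiority at one-sided 2.5% and equivalence by two one-sided tests at 5% both give 935.6, and a one-sided comparison of 10% with 15% gives 945.

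**3. The planned effect on escalation.** Expected reduction: 0.10 × 0.50 × 0.20 = 0.01, that is, 10% to 9%. With 9340 bed movements per group (section 19):

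half-width = 1.96 × √[(0.10 × 0.90 + 0.09 × 0.91) / 9340] = 1.96 × √(0.1719 / 9340) = 0.84 points.

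Difference -1.0 point, 95% CI -1.84 to -0.16, which excludes zero.

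**4. The same averted escalations on the composite.** The documents give no rate for RRT therapy, so this is an illustration. Assume that the composite counts a bed movement with at least one component. Let g be the share of averted escalations that involved RRT therapy. Those remain composite events, so the composite changes by -(1 - g) × 1.0 point.

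Take a 10% composite rate, the lowest possible when escalation alone is 10%. The interval reaches zero when (1 - g) × 1.0 equals its half-width. At 10% against 9.16% the half-width is 1.96 × √[(0.0900 + 0.0832) / 9340] = 0.84 points, so g = 1 - 0.844 = 0.156. Above about 16%, the composite interval includes zero while the escalation interval does not.

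A higher composite rate lowers that threshold. With g = 0, solving 1.96 × √{[p(1 - p) + (p - 0.01)(1.01 - p)] / 9340} = 0.01 gives p = 0.147. Above a usual-care composite rate of about 14.7%, even the full 1.0-point fall does not exclude zero.

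**5. Is the margin tested?** The final SAP expresses treatment effects on escalation as a ratio of counts and an odds ratio. Its general paragraph also plans counts and percentages by arm with a chi-square test. No adjusted risk difference is planned, and nothing is compared with the 5% margin.

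**The case against.** The strongest reply is that the primary can be inferred. The Objectives, feasibility, design and sample size passages all point to escalation. The Summary of Changes also numbers its outcomes from a list that is not in these documents and may name the primary. Both points stand in part. They show which choice fits best, and they limit the finding to these documents. They do not settle count against ever/never, and they do not explain why the endpoint listed under Primary Endpoints vanished without an entry.

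Several stronger readings are tempting, and the documents do not support them:

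- **That many models compete for primary status.** The covariate-adjusted models are labelled confirmatory and the ICU outcomes ad hoc. Two real rivals remain.
- **That the SAP reports only ratios.** Percentages by arm with a chi-square test are planned, so a crude difference can be derived.
- **That every trace of RRT therapy was dropped silently.** Blood pressure support is still modelled, and the removal of respiratory support is logged with its reason.
- **That alert volume shows the composite could rise past the margin.** The pilot summary gives "Median # of alerts to RRT, per floor, per day: 4", while section 10 speaks of 5 alerts per 12 hours per floor. No rate of therapy per alert is given, so no useful bound follows.
- **That power is unaffected by the choice of endpoint.** That could be said only of a 5-point margin with no true difference. For superiority, 9340 per group gives about 64% power at 10% against 9%, and about 50% for a 1.0-point fall from a 14.7% composite rate.

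**Conclusion.** The point holds. The protocol contradicts itself on the primary endpoint. The final SAP does not resolve this, and the change log omits the loss of the composite. The hypothesis is inconsistent in the protocol, absent from the final SAP, and the stated margin is never tested. These are matters of text and do not depend on the calculation.

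The calculation shows only that the choice can change the conclusion. It assumes that the planned 1-point effect occurs, that 9340 bed movements per group are analysed as independent, and that the composite counts bed movements with either component. It ignores clustering by unit. It also ignores the restriction to first hospitalisations, which makes the analysed number unknown. The share of averted escalations that involved RRT therapy is not known.

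A reader might infer that the composite was a poor choice or was dropped because of its results. Nothing in the documents shows either.

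**What to change.** Reconcile the two statements in section 3 with the SAP by naming one primary endpoint and one primary model. Escalation, analysed as the IPTW ever-escalated outcome, agrees best with the Objectives and with sections 7, 11 and 19. The match is not exact: the size was set in bed movements, while the SAP analyses first hospitalisations per patient, and this should be said.

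- Add an IPTW-weighted risk difference with a 95% CI, read against the section 19 margin. State one hypothesis and whether the margin is absolute or relative.
- Report the count model as secondary.
- Record in the Summary of Changes, with the reason, that the listed composite was not analysed.
- Disclose that the designation was made after data were seen.
- Report the composite, or its RRT-therapy components, alongside if the records permit.

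For escalation this needs no new data. The cost is an openly post hoc designation. The composite may not be recoverable. Section 11 planned that "Additional information provided by the RRT team on the result of the RRT intervention will be extracted from REDCap", but the Summary of Changes calls a separate RRT call tracking system unusable and does not say whether the therapy records share that problem.
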